Work performance [lost productivity due to time away from work (absenteeism) and reduced efficiency at work (presenteeism). 242 7-day work performance questionnaire. 243	13	Interview format. Varied (10-pt scale and dichotomous [yes/no] and number hours spent performing paid and unpaid work	0.73	Predictive Concurrent Construct	Caregivers will be interviewed at baseline, 3-, 6-, 9-, and 12-months to assess lost productivity.

**C.11. Health care utilization outcomes: Caregivers and patients.** Health care utilization of both caregivers and consenting HF patients will be obtained from the EMR for 12 months before and 12 months after randomization using a process of active surveillance **(Table 6)**. The Penn Data Store will monitor inpatient and outpatient activity and generate automated reports for tracking of mortality. As EMR data may be incomplete if a person is hospitalized outside the Penn health system, caregivers will be asked about their health care use when they are telephoned at 3, 6, 9, and 12 months. If the patient in their care has provided consent, we will also ask the caregiver about HF patient hospitalizations outside the Penn health system. We will ask about all major categories of use including provider visits, hospitalizations, emergency department (ED) visits,

diagnostic and therapeutic procedures, ambulance services, and home care services received. RAs blinded to study group will perform these assessments.

Table 6. Cos	Table 6. Cost Effectiveness Data to be Collected on Caregivers and HF Patients						
Variable	Definition and Comment	Measures					
QALYs	QALYs are derived from the SF-36 because the SF-6D based on the SF-36 is more discriminative than that derived from the SF-12. 	SF-36					
Hospital readmission rates	Risk-standardized all-cause readmission rates (RSRR) endorsed by the National Quality Forum  as a measure of hospital performance and aligns with published standards for statistical models used for calculation and public reporting of health outcomes and efficiency measures. 	EMR					
Days in the hospital	Captures the natural history of the multimorbid HF patient experience.  Used to describe the burden of disease from the individual and healthcare system perspectives  and in previous trials.  Maximal exposure of 365 days.	EMR					

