Statistical comparisons will be performed using generalized estimating equations (GEE) with links selected using the Pearson correlation test, the Pregibon link test, and the modified Hosmer and Lemeshow test, and families selected using the modified Park test. Estimates of average total treatment costs and QALYs will be generated separately for each group. Non-parametric 95% CIs will be determined for group differences in mean total costs using empirical sampling distributions (1,000 iterations) generated with bootstrapping methodology with replacement. We will compute a non-parametric two-sided p-value based on the empirical sampling distribution. Differences in cost and QALYs will be used to calculate the incremental cost-effectiveness ratio. Reported measures of sampling uncertainty for this ratio will include 1) the plot of the joint distribution of the difference in cost and effect on the cost-effectiveness plane, 2) the confidence interval for the cost-effectiveness ratio calculated by use of the Fieller's theorem method, and 3) the acceptability curve. Sensitivity analysis is a critical component of an economic evaluation since all assumptions and parameter estimates have uncertain precision. As more than one approach is often available to monetize outcomes, we will calculate a lower and upper bound estimate, as relevant, for the benefit (QALYs) and cost calculations. We will combine this series of sensitivity analyses to form a lower and upper bound estimate for preliminary ICER.

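### Aim 2 names no baseline covariate for the cost comparison, although a year of pre-randomisation use is collected; pre-specifying one would gain precision at little cost

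*Combined protocol and SAP*

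**What the plan says.** **Data collected.** Under C.11, health care use of caregivers is "obtained from the EMR for 12 months before and 12 months after randomization". For work performance, Table 5 states: "Caregivers will be interviewed at baseline, 3-, 6-, 9-, and 12-months to assess lost productivity". The SF-36, from which the SF-6D is derived, is also collected from caregivers at baseline (Specific Aims; C.3). Randomisation balances caregiver sex and relationship to the patient (C.4.d), not prior cost.

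**Aim 2 analysis (C.14.2).** "Statistical comparisons will be performed using generalized estimating equations (GEE) with links selected using" several named tests, and the family is chosen by another. Then: "Estimates of average total treatment costs and QALYs will be generated separately for each group". For the interval, "Non-parametric 95% CIs will be determined for group differences in mean total costs using empirical sampling distributions", with 1,000 resamples. The ICER is the cost difference divided by the QALY difference. None of these sentences names a covariate.

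**Other aims.** C.14 (Aim 1 models) and C.14.3 (Aim 3) both name the baseline value of the outcome as a covariate.

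**General rules.** C.4.d foresees control for important covariates after an initial comparison of the groups. C.14 plans a balance check after database lock and undertakes to adjust every analysis for chance imbalances.

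**Gap in the text.** The sentence that leads into the Aim 2 model breaks off in the extracted document, so part of the model description may be lost.

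**The concern.** C.14.2 lists the cost difference among the main outcomes of the economic analysis, and its sign separates dominance from a positive net cost. The documents give no power calculation, SD or target precision for it. A covariate measured before randomisation and correlated with follow-up cost would narrow its interval without further recruitment. The plan collects such a variable, uses baseline values in the other two aims, and does not say that it will do so here. If the covariates are left to the statistician, or to a balance check after lock, the precision may be lost, or the choice behind the ICER may be made with the data in hand.

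**Working it through.** **1. Sample size available.** C.13 plans 100 evaluable caregivers per arm (200 in all) and 20% attrition: 200 / (1 − 0.20) = 250, which is the stated enrolment. No Aim 2 cost figure exists to reproduce. The correlation r between prior-year and follow-up health care cost is not given, so 0.3 to 0.7 is assumed throughout.

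**2. Precision with and without the covariate.** With n per arm, and cost measured in its own SD:
- unadjusted SE = √(2/n) = √(2/100) = 0.141 (√(2/125) = 0.126 with no attrition);
- adjusted SE = √(2/n) × √(1 − r²);
- equivalent n per arm = n / (1 − r²).

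| Assumed r | Variance factor 1 − r² | Adjusted SE, n = 100 | Interval narrower by | 100 per arm acts like |
|---|---|---|---|---|
| 0.3 | 0.91 | 0.135 | 5% | 110 |
| 0.5 | 0.75 | 0.122 | 13% | 133 |
| 0.7 | 0.51 | 0.101 | 29% | 196 |

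**3. The same gain as power.** A comparison with 80% power unadjusted (two-sided 5%) would have power Φ[(1.96 + 0.8416)/√(1 − r²) − 1.96], which is 84%, 90% or 98%.

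**4. Skewed costs.** A simulation drew lognormal costs (log-scale SD 1.2, 100 per arm, 4,000 trials) and adjusted linearly for prior cost. Log-scale correlations of 0.3, 0.5 and 0.7 became about 0.19, 0.36 and 0.57 on the cost scale. The ratio of adjusted to unadjusted SE was 0.97, 0.92 and 0.80. The gain survives skewness, but it follows the cost-scale correlation, which is lower.

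**5. Chance imbalance is the same quantity.** At 100 per arm, a one-SE imbalance in prior cost (0.141 SD) moves an unadjusted cost difference by r × 0.141, that is 0.04, 0.07 or 0.10 SD. The unadjusted variance splits as 2/n = (1 − r²)(2/n) + r²(2/n). For r = 0.5 this is 0.0200 = 0.0150 + 0.0050, and 0.0050 is the square of the 0.071 SD carry-over. Adjustment removes that second term. It is the precision loss in step 2, not a further effect.

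**6. Does the general rule already supply the covariate?** It depends on an imbalance being seen and sets no threshold, whereas the gain in step 2 does not depend on any observed imbalance. It names neither prior cost nor work performance. It does not say how adjustment would enter the bootstrap or the ICER.

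**The case against.** A reader might infer that Aim 2 compares unadjusted means and bootstraps a raw difference. The documents do not support that:
- Neither term is used, and means given for each group can be model-based.
- GEE is a regression method. With arm as the only regressor, every link would fit the same two means and the link tests would have nothing to choose between, so further regressors may be intended. These need not be baseline covariates.
- H2b is labelled a secondary outcome, and the mixed-model paragraph of C.14 gives primary and secondary outcomes a baseline covariate. C.14.2 sets out its own methods for costs, so this leaves an ambiguity rather than an answer.
- C.4.d and C.14 promise covariate control, and some of the Aim 2 text is lost.

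A reader might also infer that chance imbalance biases the ICER. Under randomisation it does not: an unadjusted bootstrap interval already reflects that variation (step 5).

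The size is open to challenge too. C.11 concedes that "EMR data may be incomplete if a person is" hospitalised outside the health system. The calls that fill this gap are made only after randomisation, so prior use is the less complete measure and r is likely to be reduced. Total cost also contains intervention and productivity costs, to which an r for health care cost does not apply.

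All of this stands. It limits the point to one about pre-specification and precision. It does not supply the missing covariates.

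**Conclusion.** The point holds as a gap in specification. The readable Aim 2 text names no baseline covariate for the cost GEE, the bootstrapped difference or the ICER, although suitable variables are collected and the other aims use theirs. An analysis without them would be valid but less precise. The variance of the health care cost difference would fall to 0.91, 0.75 or 0.51 of its unadjusted value for r of 0.3, 0.5 or 0.7. These correlations are assumptions, and the lower end is the more plausible. The factors apply to the health care component, not to total cost. The conclusion is also subject to the lost text before the GEE sentence: if covariates are named there, only the link to the bootstrap and ICER remains to be stated. The change is worth making, but the trial's validity does not turn on it.

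**What to change.** In C.14.2, before database lock:
1. Name each caregiver's EMR-based cost over the 12 months before randomisation as a covariate in the cost GEE, and baseline work-performance loss as a covariate for the productivity component.
2. Derive the adjusted difference in arithmetic mean cost from the fitted model.
3. Adjust QALYs for baseline SF-6D, so that numerator and denominator of the ICER are treated alike.
4. Resample caregivers within arm and refit the models in every bootstrap resample. Use the adjusted differences for the cost-effectiveness plane, the ICER and the acceptability curve.
5. Report the unadjusted differences beside the adjusted ones.

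The cost is a few sentences in the plan and a little more analysis work, with no new data collection. Prior-year EMR cost is an imperfect covariate because outside care may be missed. It is nevertheless fixed before randomisation and measured in the same way in both arms, so its imperfection reduces the gain without biasing the comparison.

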- **C.9. Caregiver Characteristics and Outcomes.** *On enrollment*, the RA will collect self-report data from caregivers using encrypted laptop computers. Data will be entered directly into the REDCap database as collected, with data entry screens designed to incorporate range checks and concurrent checks to minimize errors. Caregiver burden will be measured using the Dutch Objective Burden Inventory (alpha coefficient 0.81-0.84, construct validity), which measures the full range of activities required to care for HF patients (demand) as well as the burden associated with these demands. Quality of the relationship with the patient; social determinants of health; and demographic, caregiving, and clinical characteristics will be gathered from caregivers at enrollment only. *At 3, 6, 9 and 12-months* post randomization we will telephone caregivers and collect self-report data on self-care, stress, coping, and health status (**Table 5**). At 12 months we will measure QALYs. These data will be obtained by interview and entered directly into REDCap using encrypted laptop computers. Self-report instruments with demonstrated cultural-sensitivity and prior validity testing in caregiving samples were chosen, and measures are as brief as possible to minimize burden.
- **C.10. HF Patient Characteristics**. With patient consent, HF patient demographic and clinical characteristics will be abstracted from the medical record at enrollment. Duration of HF will be measured in months. All comorbid conditions will be noted and classified using the Charlson Index.  Physician ratings of New York Heart Association functional class as noted in the EMR at enrollment will be used to describe HF patients. The SF-6D will be administered to HF patients at baseline and 12 months to obtain QALYs. 

Table 5. Caregiver Outcome	e Varial	oles and Measurement			
Definition and Measure	Items	Item responses	Reliability	Validity	Comments
Self-care (behaviors undertaken to maintain health). Health Self-Care Neglect (HSCN) scale  and the short Health-promoting lifestyle profile (HPLP) II. 	10 30	HSCN dichotomous. HPLP 4-point Likert scale; higher score = more healthy behavior.	0.76 0.90	Content Criterion	The HSCN has not been widely tested so we augment this measure with the widely-used Health-promoting lifestyle profile II. To minimize burden, we will use the short form.

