To assess changes in each of the primary and secondary outcomes over time, separate mixed effects regression models will be generated with SAS Proc Mixed. 265 We are not powered for secondary outcomes (e.g., stress, coping, health status), but we will examine effect sizes and confidence intervals (CIs) to determine if lack of power is driving nonsignificant results. Mixed models can account for correlation between repeated measures and handle non-excessive MAR or MCAR data better than traditional models and allow for use of time-independent and time-dependent covariates. Both random slopes and random intercepts will be modeled to represent deviations from the average, or fixed-effect, slope over time and intercept, respectively. REML will be used for parameter estimation and the most appropriate covariance structure will be examined. Scores will be analyzed as repeated observations, with mean-centered baseline outcome scores serving as a covariate. Other predictor variables will include group, assessment time, and the interaction of group time (primary effect of interest). Baseline measures and group will be analyzed as time-independent covariates. The evaluation of differences in outcome profiles over time according to group will rely on the group x time interaction terms, while differences by the balancing variables will rely on the mixed-effects modeling of higher order interaction terms. 267-270 Statistical significance for individual intervention contrasts will be evaluated for each outcome, applying the Benjamini & Hochberg method to control for the type I error rate at 5%. The Akaike information criterion (AIC) will be used to evaluate overall model fit and to select the best-fitting longitudinal change pattern. We expect the groups to be balanced on baseline characteristics due to randomization; however, imbalances that occur by chance will be adjusted for in all analyses. Time-dependent covariates of perceived stress and potential moderating effects of natural support or an intervening hospitalization will be examined in exploratory models. Using methods described above, time-specific contrasts will be estimated to evaluate differences in outcome within groups at 9 and 12 months.

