**C.14.3.** Aim 3 (Exploratory): To explore the effect of caregiver outcomes (self-care, stress, coping, health status) on HF patient outcomes. We hypothesize that at 12 months, HF patients whose caregivers improve vs. not improve in self-care (regardless of group) will have H3a: Lower hospitalization rates; H3b: Fewer hospital days; H3c: Lower mortality rates; and H3d: Higher QALYs measured with the SF-6D. We will analyze number of hospitalizations and days in the hospital using GEE regression models with the Poisson distribution as the working outcome distribution. GEE allows for modeling of the marginal distribution of each outcome variable as a function of the caregiver predictor of interest over time, and accounts for the likely correlations of the repeated outcome measures for each participant. An approach similar to that described for Aim 1 will be used within the GEE framework (different correlation structures will be examined, baseline outcomes will be included as a covariate).

We will measure time to death from date of the caregiver's enrollment in the study to the date of patient death. Patients remaining free from an event will be censored at their last follow-up. Kaplan-Meier estimates will be plotted to provide a visual demonstration of time to death by group (categorized caregiver outcomes), and the log-rank test will be used for comparisons. GEE and frailty type multivariable modeling will be applied to time-to-event data within the context of equally spaced time intervals. This approach allows for the addition of a random effect to a general Cox proportional hazards model to account for the likely correlation of repeated measures for each study participant while also accounting for censoring.

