QALYs will be analyzed using mixed effects regression modeling. As described above, scores will be analyzed as repeated observations, with mean-centered baseline outcome scores serving as a covariate. Other predictor variables will include time-dependent caregiver variables, assessment time, and the corresponding two-way interaction term (primary effect of interest). Statistically significant findings will be concluded on the basis of a two-sided 0.05 level of significance, recognizing these analyses are exploratory in nature and findings will be used to generate hypotheses. Finally, we will examine the effect of caregiver outcome on HF patient outcomes in patient-caregiver dyads using the Actor-Partner Interdependence Model.

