#### **Recruitment and Retention Plan**

We plan to enroll a consecutive sample of 250 informal caregivers (125/arm) of heart failure (HF) patients (HF caregivers). The main enrolment site is the Penn Heart and Vascular Center (PHVC), the largest outpatient HF clinic in the Philadelphia region and a site at which the Principal Investigator (PI) has established relationships and success in past recruitment of participants. If recruitment is slower than expected, we will identify caregivers visiting HF patients hospitalized at one of three University of Pennsylvania Health System (UPHS) sites.

We anticipate identifying 100 unique HF patients each month, most of whom will have caregivers. Based on our prior research, we anticipate that 90 will have caregivers and 70% of these (63 caregivers) will be eligible, and 15% will enroll. Thus, we estimate enrolling 10 caregivers per month. Using this number, we anticipating needing at least 25 months for enrollment, but we have conservatively allowed 30 months for enrollment and five years to complete the study.

In addition to caregivers, we want to enroll at least 40 caregiver-patient dyads. We understand the challenges of enrolling dyads, but 40 dyads is sufficient to provide reliable parameter estimates for this exploratory aim. The effort of HF patient participants is minimal. They will not receive an intervention. They will be asked to provide informed consent to allow us to access their electronic medical record (EMR) to collect clinical information and track events and, in the case that patients receive care outside the Penn health system, for the caregiver to report on patient health care resource use. At the end of the study period (12 months), the HF patients will be asked to provide data on quality adjusted life years (QALYs).

We will have a study Research Assistant (RA) on site during PHVC clinic hours so that the RA can meet the informal caregiver in person because we anticipate that a face-to-face meeting will maximize enrollment. We plan to seek a HIPAA waiver to screen the daily appointment schedule to identify every patient with a potentially eligible caregiver (e.g., living within 50 miles of the research office). [name], a co-investigator on the study, will ask clinic staff to identify potential caregiver participants (e.g., speak English) and determine their willingness to speak with research staff about the study.

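### Aim 3: the caregiver-by-time effect on patient QALYs (H3d) cannot be estimated from one follow-up SF-6D, and the mortality comparison (H3c) needs a stated rule for deaths before caregivers are classified

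*Combined protocol and SAP*

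**What the plan says.** **H3d, patient QALYs.** C.14.3 describes a mixed model: "As described above, scores will be analyzed as repeated observations, with mean-centered baseline outcome scores serving as a covariate". It then names the target effect: "Other predictor variables will include time-dependent caregiver variables, assessment time, and the corresponding two-way interaction term (primary effect of interest". On data collection, C.10 states: "The SF-6D will be administered to HF patients at baseline and 12 months to obtain QALYs". The Recruitment and Retention Plan mentions only the later assessment: "At the end of the study period (12 months), the HF patients will be asked to provide data on quality adjusted life years (QALYs". The Aim 1 model in C.14, which C.14.3 points back to, says: "Both random slopes and random intercepts will be modeled to represent deviations from the average".

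**H3c, mortality.** The hypothesis compares "HF patients whose caregivers improve vs. not improve in self-care (regardless of group"). The time origin is given as: "We will measure time to death from date of the caregiver's enrollment in the study to the date of patient death". The comparison is: "Kaplan-Meier estimates will be plotted to provide a visual demonstration of time to death by group (categorized caregiver outcomes), and the log-rank test". Section C.15, item 4, says a caregiver leaves the study if the patient dies. No section says what change counts as improvement, which visit classifies the caregiver, or what happens to a dyad whose patient dies before that visit.

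**Scale and status.** C.4.a plans at least 40 dyads. C.14.3 tests at a two-sided 0.05 level and labels the results exploratory and hypothesis-generating.

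**The concern.** The H3d wording fits the caregiver data of Aim 1, which have four follow-up visits. Patients have one. An interaction with time needs at least two distinct response times, so the effect that the plan calls primary for H3d has no estimate. An analyst following the text would have to choose another effect after seeing the data.

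For H3c, group membership is decided after the clock has started. A patient must survive to the classifying visit for the caregiver to be observed as improved or not. How earlier deaths are handled can therefore create a difference where none exists, in either direction, and the plan leaves that choice open.

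Aim 3 is where the plan examines patient outcomes. At stake are the hypotheses it generates, not the trial's primary or secondary conclusions.

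**Working it through.** The plan gives no power, precision or effect size for Aim 3, so there is no figure of its own to reproduce.

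**1. H3d design.** Let Y0 and Y12 be a patient's SF-6D at baseline and 12 months, C the caregiver variable and t assessment time. The written model is

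Y12 = b0 + b1(Y0 − mean) + b2·C + b3·t + b4·C·t.

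Every response has t = 12, so this becomes

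Y12 = (b0 + 12·b3) + b1(Y0 − mean) + (b2 + 12·b4)·C.

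Five coefficients are written and three combinations are estimable: rank 3 of 5. The interaction b4 cannot be separated from b2. The sum b2 + 12·b4 is estimable and equals the caregiver coefficient of an ANCOVA of Y12 on Y0 and C.

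**2. Other readings of H3d.**
- Baseline also kept as a response: the fixed effects have rank 5 of 5, but C.14.3 gives baseline the covariate role. If the Aim 1 random intercept and slope were carried over, four covariance parameters (two variances, a covariance, a residual) would have to come from the three distinct elements of a 2×2 matrix.
- Visit timing: C.15 allows caregiver calls two weeks either side. If that window also applied to patients, the interaction would be estimable only through scatter in dates, with a standard error about 39 times that of a 3/6/9/12-month design.

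**3. H3d precision.** C.15 says half of HF patients die within 5 years. Assuming a constant hazard, h = ln 2/5 = 0.1386 per year.
- Alive at 12 months: 40 × exp(−0.1386) = 40 × 0.8706 = 34.8.
- If the 20% attrition of C.13 applies and includes deaths: 40 × 0.8 = 32.
- If it comes on top of deaths: 34.8 × 0.8 = 27.9.

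For the ANCOVA coefficient (t test, n − 3 degrees of freedom, noncentrality √n·r/√(1 − r²)), 80% power at two-sided 0.05 needs noncentrality of about 2.9. That gives partial r of about 0.44 at n = 35, 0.46 at n = 32 and 0.48 at n = 28.

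**4. H3c under no effect.** Same hazard, 12 months, classification at month 6, 50% of classified caregivers improving (assumed). Per enrolled patient:
- Deaths before month 6: 1 − 0.9330 = 0.0670. Deaths in months 6 to 12: 0.9330 − 0.8706 = 0.0625 (from unrounded values).
- Total person-years: (1 − 0.8706)/0.1386 = 0.934.
- Improved group: deaths 0.5 × 0.0625 = 0.0312; person-years 0.5 × (0.5 × 0.9330 + 0.0625/0.1386) = 0.459; rate 0.068.
- Remainder, with early deaths coded not improved: deaths 0.0670 + 0.0312 = 0.0982; person-years 0.934 − 0.459 = 0.475; rate 0.207.
- Ratio: 0.068/0.207 = 0.33. The same arithmetic gives 0.41 with 30% improving and 0.23 with 70%.

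| Early deaths | Null rate ratio (50% improving) | Simulated log-rank false positives, 40 dyads |
|---|---|---|
| Coded not improved | 0.33 | about 16% (2.4% at 30% improving, 41% at 70%) |
| Coded improved | 1/0.33, about 3 | about 18% |
| Excluded | 1 | about 2% |

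Exclusion gives 1 because both groups are event-free to month 6 and share one hazard afterwards.

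**5. Deaths available at 40 dyads.** Expected in 12 months: 40 × 0.1294 = 5.2. Before month 6: 40 × 0.0670 = 2.7. After month 6: 40 × 0.0625 = 2.5. With classification at month 12, every death comes first and none remains.

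**The case against.** **H3d loses little in practice.** This stands. With the redundant columns dropped, the written model is already an ANCOVA, and its caregiver coefficient is the 12-month effect of interest. A reader might infer that the caregiver effect on patient QALYs cannot be studied at all; step 1 shows otherwise. What fails is the effect named as primary.

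**The covariance may be a non-issue.** A reader might also infer that the model fails on its random effects even if baseline is a response. That depends on importing the random slope from Aim 1. The cross-reference in C.14.3 introduces repeated observations with a baseline covariate and does not mention slopes, and C.14 leaves the covariance structure to be examined. The main finding does not rest on this.

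**Other Aim 3 models are planned.** C.14.3 also lists GEE and frailty models over equal time intervals and an Actor-Partner Interdependence Model. The time-to-event models could carry a caregiver status updated at each visit, but the text does not say they will, and the Kaplan-Meier and log-rank comparison uses groups.

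**Early deaths may simply be excluded.** C.15 drops the caregiver when the patient dies, which fits exclusion at least as well as any coding, and exclusion is unbiased. This stands, so H3c is a missing rule rather than a demonstrated bias.

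**Forty dyads is a floor.** True: expected deaths rise in proportion to the number of dyads. The aliasing in H3d does not depend on sample size.

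**Conclusion.** H3d is wrong as written: with one post-baseline SF-6D per patient and baseline as the covariate, the caregiver-by-time effect cannot be estimated. The exploratory label does not change that. The estimable quantity is the baseline-adjusted caregiver effect at 12 months among surviving patients with a score. This conclusion is firm and uses only the schedule in C.10 and the model in C.14.3. The survivor counts and detectable correlations assume a constant hazard from the five-year figure and the minimum of 40 dyads.

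The H3c point is secondary and conditional. A reader might infer that the mortality comparison is biased in favour of improving caregivers. The documents do not support that, because they state no coding: under no effect the month-6 ratio is about 0.33, about 3 or 1 according to a rule not yet written. These values also assume that half of caregivers improve and that improvement is unrelated to survival. What is established is that the rule is missing and that it can decide the result.

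**What to change.** **H3d.** For this outcome, drop assessment time, its interaction and the random effects. Name as the H3d effect the caregiver coefficient in an ANCOVA of 12-month SF-6D on baseline SF-6D, with caregiver self-care classed as improved or not improved from baseline to month 6, matching the hypothesis. Report continuous self-care change alongside. State that the result describes surviving patients with a 12-month score. Reconcile C.10 with the Recruitment and Retention Plan on whether patients give a baseline SF-6D, since the adjustment needs it.

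**H3c.** Name month 6, the Aim 1 primary visit, as the single landmark. Start the clock there, among patients then alive. Define improved in advance as a stated change in the Health Self-Care Neglect score from baseline. One candidate is the 1.12-unit difference that C.13 calls clinically meaningful; on a count of ten yes/no items that is a fall of at least 2 points. Do not classify at month 12. Report deaths before month 6 descriptively, assigned to neither group.

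**Cost.** SAP wording only, with no added visits or data if the baseline SF-6D is collected as C.10 says. The landmark leaves about 2.5 expected deaths at 40 dyads, so its log-rank test is descriptive. The ANCOVA can reliably detect only fairly strong associations (partial r of about 0.44 to 0.48).
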